4.1 Overview

This is an international, multicentre, non-interventional, prospective, single-arm study. This study will be conducted in up to 50 centres in Austria and Germany. A total of 150 participants will be included in the study. Participants will be treated and monitored in accordance with usual medical practice during their participation in this study.

The expected duration of the recruitment period will be 18 months. Participants will be followed for a maximum of 18 months (observation period) while they receive cabozantinib as per the SmPC.

Participants prematurely discontinuing cabozantinib (i.e. within the first 15 months of observation period) and initiating a subsequent treatment will be followed up approximately 3 months after the treatment switch to collect effectiveness data for the new LoT. Enrolment in the study is possible if cabozantinib treatment started up to 4 weeks prior to enrolment. The data for Visit 1 will be captured retrospectively and starting at Visit 2 data will be collected prospectively including hrQoL baseline assessment.

To avoid selection bias in participant recruitment, investigators will offer enrolment to all eligible participants consecutively to achieve their recruitment target during a restricted and defined period. This includes patients who have stopped cabozantinib treatment within their first 4 weeks to avoid selection bias. But, if consecutive enrolment is not feasible (e.g. administrative constraints), an alternate enrolment schedule will be permitted and will have to be documented before the first participant is enrolled. The investigators will have to follow the same recruitment pace until achievement of his/her recruitment target.

4.2 **Population Characteristics**

One hundred and fifty (150) adult participants with unresectable or metastatic, well -differentiated epNET and pNET who have progressed following at least one prior systemic therapy other than SSA, and who are prescribed cabozantinib tablets according to the SmPC prior to entry into the study will be included in Austria and Germany.

Further details of the study population are provided in Section 5.

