4.7 Study Duration/Observation Period

The expected study duration is 3 years, with an 18-month enrolment period from first participant, first visit. The EoS is expected to be a maximum 18 months after the last participant has been enrolled.

The study will be considered to have started when the first participant has signed informed consent.

The study will be considered to have ended after the last participant's data has been collected.

The study observation period starts from participants signing the informed consent and continues until Visit 9 (Month 18). Participants discontinuing cabozantinib treatment and starting a new LoT during the first 15 months of cabozantinib treatment are passing over into the follow-up, which is approximately 3 months after discontinuation of cabozantinib.

Participants will be followed until the end of observational period (i.e. a maximum of 18 months after Visit 1) or withdrawal of consent, or death, whichever occurs first.

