4.8 Participant Information

Prior to enrolment of a participant in this study, the investigator, or a person designated by the investigator, will explain the nature and purpose of this data collection to each participant. As all assessments and procedures will be conducted in accordance with routine/standard clinical practice, participation in the study does not convey any additional risks or burdens for the participant. However, the participant will be provided with information on the benefits and risks of their medical treatment.

Written informed consent must be obtained prior to participant enrolment and prior to any data being entered in the study database. Sufficient time should be allowed to discuss any questions raised by the participant. The participant should be allowed as much time as they need to consider their decision.

The sponsor will provide an informed consent form (ICF), in German language easily understood by the participant. Each participant's original consent form, personally signed and dated by the participant, and by the person who conducted the informed consent discussion, will be retained by the investigator. The investigator will supply all enrolled participants with a copy of their signed informed consent. None of these informed consents will be collected by the sponsor.

The consent form will be revised during the study if important new information becomes available.

PAGE 28/52

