6.1.2 Secondary Effectiveness Endpoints

Objective response rate (ORR):

ORR is defined as proportion of participants who achieve CR or PR determined based on radiographic assessments between the date of the first dose of cabozantinib and the date of PD or date of subsequent therapy.

Quality of life (hrQoL):

See Section 6.3.

Cabozantinib dosage adjustment and schedule:

- Starting dose, all dose modifications according to frequency, timing, reason for adjustment, type of adjustment and duration of modified dosing, specifically:
 - Frequency of dose reductions and reason (specifically adverse events).
 - Frequency of dose interruptions and reason (specifically adverse events).
 - Frequency of treatment discontinuations and reason (specifically adverse events).

PROTOCOL FINAL V1.0: 30 JULY 2025

PAGE 30/52

Duration of treatment (DoT):

DoT during cabozantinib treatment phase, defined as time from first intake of cabozantinib until date of permanent cabozantinib treatment discontinuation.

Frequency of therapy switch and subsequent therapy:

Frequency of therapy switch is defined as permanent discontinuation of cabozantinib treatment within the cabozantinib treatment phase and start of a next LoT as well as nature of next LoT.

Disease control rate (DCR) after switch to next LoT:

DCR is defined as proportion of participants who within 3 months after switch to next LoT achieve CR, PR or SD determined based on radiographic assessments between the date of the first dose of new treatment until the date of progressive disease (PD) or date of further subsequent therapy.

Time to next treatment (TTNT):

Time from the first dose of cabozantinib to the first dose/administration of the subsequent therapy.

Landmark PFS at 12 months and 18 months:

PFS during cabozantinib treatment phase is defined as time from first intake of cabozantinib until PD (as assessed by the investigator per radiological and/or clinical tumour assessment) or death from any cause. Landmark PFS will be determined at 12 and 18 months and if the number of events allows, the median PFS will be presented.

Biomarker assessments:

Determination of CgA and NSE levels by local labs as per local routine.

- CgA-levels at each visit, CgA was assessed.
- NSE-levels at each visit, NSE was assessed.

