8.2 Definition of Analyses Populations

Enrolled population: All participants enrolled.

Full Analysis Set (FAS) / A Safety population

All eligible participants treated with cabozantinib within this

non-interventional study.

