8.4.3.2 Secondary Effectiveness Analysis

Objective response rate (ORR):

ORR is defined as the proportion of participants who achieve CR or PR determined based on radiographic assessments between the date of the first dose of cabozantinib and the date of PD or date of subsequent therapy.

The proportion of participants with ORR will be calculated by counting all participants who have PR or CR at any post-baseline TA and dividing them by the number of participants in the FAS with at least one post-baseline TA. Patients who are treated with cabozantinib beyond progression but have not had PR or CR prior to disease progression, will be considered to have no PR or CR, even if they achieve PR or CR after PD. ORR will be provided with the corresponding 95% CI.

In a secondary analysis, the ORR will be calculated similarly except that the count of participants who have PR or CR at any post-baseline TA will be divided by the number of participants in the FAS.

QLQ-C30 global and subscale scores for each visit at which hrQoL was assessed:

See Section 8.4.5.

QLQ-GINET21 subscale scores for each visit at which hrQoL was assessed:

See Section 8.4.5.

Duration of treatment (DoT) and time to next treatment (TTNT):

Both DoT and TTNT will be presented descriptively as quantitative parameters. TTNT will be presented for the subgroup of participants with a subsequent therapy.

Progression-free survival:

PFS will be estimated on the FAS, using the Kaplan-Meier method and plotted as a survival curve.

The survival rates at 12-month follow-up and 18-month follow-up will be estimated and presented with their 95% CIs.

If the number of events allows, the median PFS, first and third quartiles with their two-sided 95% CIs will be presented.

Biomarker assessments:

CgA levels at each visit where CgA was assessed will be summarised for each visit by descriptive statistics providing n, mean, 95% CI of the mean, StD, median, minimum, and maximum. NSE levels at each visit where NSE was assessed will be summarised for each visit by descriptive statistics providing n, mean, 95% CI of the mean, StD, median, minimum, and maximum.

Switch to subsequent therapy:

The proportion of participants who permanently discontinued cabozantinib and started a new LoT will be described, as well as the types of therapies in this subsequent line.

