8.4.4 Safety Analysis

Safety analyses will be performed on the Safety population.

During the Treatment Period (Visit 2 to Visit 9), all treatment-emergent AEs including nonserious AEs and SAEs and SS including pregnancy will be collected.

Analysis of AEs

A treatment-emergent AE is defined as any AE that occurs after the first dose of study treatment if:

- It was not present prior to receiving the first dose of study treatment; or
- It was present prior to receiving the first dose of study treatment but the intensity increased during the active phase of the study.

The focus of analysis of this study will be the duration of the Treatment Period, i.e. up to 30 days after the permanent discontinuation of cabozantinib.

An overall summary table of all AEs (including fatal events) will be presented with the number and proportion of participants and the number of events, including frequency of SAEs, drug-related AEs and drug-related SAEs. Summary incidence tables of all AEs, SAEs and AEs by relationship and intensity/grade to study drug will be provided, classified by primary System Organ Class (SOC) and Preferred Term (PT).

All AEs will be coded according to the Medical Dictionary for Regulatory Activities (MedDRA) and will be classified by MedDRA PT and SOC.

All safety data will be included in the participant data listings, such as listings of all AEs, SAEs, AEs leading to study drug withdrawal, AEs leading to dose reduction or interruption and listings of deaths.

Analysis of "Special Situation"

SSs will be listed separately, and summary incidence tables will be provided. The AEs associated with SSs will be described.

PAGE 37/52

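### PFS is timed from first intake but consent may come up to 4 weeks later, so deaths before consent cannot be seen; the bias is small and favourable, and the plan neither handles nor shows it

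*Protocol*

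**What the plan says.** The pieces stand in different sections of the protocol:

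- **Time origin.** Section 6.1.2: "PFS during cabozantinib treatment phase is defined as time from first intake of cabozantinib until PD", or death from any cause.
- **Estimator and population.** Section 8.4.3.2: "PFS will be estimated on the FAS, using the Kaplan-Meier method and plotted as a survival curve". Rates at 12 and 18 months are reported with 95% CIs. Entry after time zero is not mentioned.
- **Entry window.** Section 4.1: "Enrolment in the study is possible if cabozantinib treatment started up to 4 weeks prior to enrolment". Visit 1 is then captured retrospectively.
- **Condition for entry.** Section 4.8: "Written informed consent must be obtained prior to participant enrolment and prior to any data being entered in the study database". Section 5.1 also requires capacity to consent. Section 4.7 adds: "The study observation period starts from participants signing the informed consent".
- **Partial remedy.** On consecutive recruitment, Section 4.1 says: "This includes patients who have stopped cabozantinib treatment within their first 4 weeks to avoid selection bias".
- **Safety.** AEs are collected from first intake (Section 9.2.1). Section 8.4.4: "An overall summary table of all AEs (including fatal events) will be presented".
- **Populations.** Section 8.1 calls a participant treated if at least one intake took place during the study. Section 8.2 defines the FAS, which is also the safety population, in similar terms: "All eligible participants treated with cabozantinib within this" non-interventional study.

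**The concern.** A participant who consents some days after first dose must have been alive on the day of consent. A Kaplan-Meier estimate that counts everyone at risk from first intake treats the days before consent as days on which that participant could have been seen to die. This is left truncation on the death component of PFS. A patient who died in that interval is in neither numerator nor denominator.

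The protocol recognises selection in this window and admits patients who stopped treatment early. It has no counterpart for patients who died or became unable to consent, and retrospective capture of Visit 1 cannot recover them because consent has to come first.

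Three results lean the same, favourable way: PFS, the secondary DCR that divides by the whole FAS, and the fatal events in the AE summary. A reader of that summary would take it to cover the time from first dose for everyone. For late enrolees it cannot do so with respect to death, and they are pooled with participants who consented by Day 1.

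The population wording can add to this. Read literally, Sections 8.1 and 8.2 drop a participant whose last intake preceded consent, which is the patient Section 4.1 sets out to keep.

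**Working it through.** **The plan's own figure.** The protocol states no precision for PFS. Its one precision figure, in Section 8.3, is ±7.5 points for the DCR. With p = 145/198 = 0.732 and n = 150 × 0.9 = 135, the half-width is 1.96 × √(0.732 × 0.268 / 135) = 7.5 points, so it reproduces.

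**Inputs from the protocol.** Median PFS 8.4 months (epNET) and 13.8 months (pNET), Section 2.3; maximum delay 28 days, Section 4.1; 150 participants; expected DCR 73%, Section 8.3.

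**Assumptions, because the protocol gives no figures.** Mortality d in the first 28 days is 1% to 3%. The share f who consent after first dose is 50% to 100%. Their delay is uniform over 0 to 28 days, the early death hazard is constant, and PFS is exponential.

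**Step 1, deaths that cannot be seen.** With uniform delay and constant hazard, half of the first-28-day deaths among late enrolees fall before consent. The missed share of all such deaths is f/2: 25% at f = 50% and 50% at f = 100%. The share of the starting cohort lost is m = f × d / 2.

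**Step 2, effect on the estimates.** Every lost patient had a PFS event before 12 months, so the analysis from first intake estimates S(12)/(1 − m). The excess is S(12) × m/(1 − m).

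- epNET: S(12) = exp(−ln 2 × 12/8.4) = 0.371
- pNET: S(12) = exp(−ln 2 × 12/13.8) = 0.547
- Secondary DCR, taking 73% as the true value: excess 0.73 × m/(1 − m)
- Missed deaths per 150 enrolled: 150 × m/(1 − m)

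| d | f | m | Missed deaths per 150 | 12-month PFS, epNET (points) | 12-month PFS, pNET (points) | Secondary DCR (points) |
|---|---|---|---|---|---|---|
| 1% | 50% | 0.0025 | 0.38 | +0.09 | +0.14 | +0.18 |
| 1% | 100% | 0.0050 | 0.75 | +0.19 | +0.28 | +0.37 |
| 3% | 50% | 0.0075 | 1.13 | +0.28 | +0.41 | +0.55 |
| 3% | 100% | 0.0150 | 2.28 | +0.57 | +0.83 | +1.11 |

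**Step 3, set against sampling error.** The 95% half-width for 12-month PFS at n = 150 without censoring is 1.96 × √(0.371 × 0.629 / 150) = 7.7 points (epNET) and 1.96 × √(0.547 × 0.453 / 150) = 8.0 points (pNET).

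**Step 4, does delayed entry remove it?** In a simulation of 400,000 patients (epNET median, f = 50%, d raised to 5% to make the effect visible), true 12-month PFS was 35.3%. Kaplan-Meier from first intake with pre-consent deaths missing gave 35.7%. Kaplan-Meier with entry at consent gave 35.3%.

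**Primary DCR.** Section 8.4.3.1 divides by FAS participants with at least one post-baseline tumour assessment, and imaging is expected about every 3 months (Section 4.5). A patient who dies in the first month will usually have no such assessment and leaves that denominator whenever consent was given.

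**The case against.** The case against is strong on size and scope.

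- **Not all first-month deaths are lost.** A reader might infer that they are structurally absent. They are not: participants who consent by Day 1 contribute all of theirs, and late enrolees contribute any after consent. Table 4-1 places Visit 1 at Day 1, and the protocol gives no share of late enrolees. This stands.
- **PFS as a whole is not truncated.** If every early PFS event were unobservable and everyone consented at week 4, epNET 12-month PFS would read 40.1% where 37.1% is true. The documents do not support that reading. Progression before consent does not bar enrolment, recruitment is meant to be consecutive, and early stoppers are admitted. Only death and loss of capacity to consent are truncated.
- **The primary DCR is not materially biased by late entry.** Its denominator rule already removes most early deaths.
- **The effect is small.** It is below 1 point against a half-width near 8, on a descriptive secondary endpoint. No first-month fatality rate is defined as an endpoint, and Section 9.1.2 gives death from disease progression as an example of what is not an SAE, so some early deaths would not reach the AE summary even if seen.
- **The SAP could deal with it.** Delayed-entry Kaplan-Meier is still Kaplan-Meier, and Section 8 leaves detail to the SAP. That is fair as to where the change is written. The protocol itself nevertheless fixes the origin, the population and the entry window that together create the problem.
- **Delayed entry has its own weakness.** It discards progression observed before consent and assumes that the timing of consent is unrelated to prognosis. This is a good reason not to let it replace the planned curve.

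What remains is a bias of known direction in the death component, which the protocol does not acknowledge.

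**Conclusion.** The point holds in limited form. Among patients not yet consented, deaths and loss of capacity to consent between first dose and consent cannot be observed. This favours PFS, the secondary FAS-denominator DCR and the fatal-event count.

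Under the stated assumptions, 12-month PFS is about 0.1 to 0.8 points too high and the secondary DCR about 0.2 to 1.1 points. One quarter to one half of first-28-day deaths go unseen, which is 0.4 to 2.3 per 150 enrolled. These figures cover deaths only and scale with two quantities the protocol does not give, early mortality and the share of late enrolees.

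For PFS alone this would be minor. The better reason to act is that a safety summary presented as running from first dose pools participants whose early deaths can be seen in full with others whose early deaths cannot.

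**What to change.** 1. **Section 8.4.3.2.** Keep the Kaplan-Meier curve from first intake. Beside it, add a Kaplan-Meier analysis in which each participant who consents after first dose enters the risk set on the consent date, or one restricted to participants who consented by Day 1. List participants whose progression preceded consent, since the delayed-entry curve leaves them out.
2. **Section 8.4.4.** Show fatal events and AEs of the first 28 days separately for participants who consented on or before first dose and for those who consented later.
3. **Sections 8.1 and 8.2.** Reconcile the definitions of treated participant and FAS with Section 4.1, so that a participant who stopped before consent stays in the FAS and safety population.

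Items 1 and 2 need no new data: consent date and cabozantinib start date are both recorded at Visit 1 (Section 4.5). The cost is a little programming, a few lines of text, and slightly wider intervals early in the added curve.

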	• To describe the potential impact of cabozantinib treatment on NET biomarkers.							
	• To describe the time to next treatment (TTNT) for cabozantinib.							
	• To describe the progression free survival (PFS).							
	Exploratory objectives							
	To describe supporting measures.							
	• To describe potential correlations between effectiveness outcomes or quality of life and occurrence of AEs, dose reduction or supportive measures.							
Rationale	Neuroendocrine tumours (NETs) are rare, heterogeneous neoplasms originating from cells of the diffuse neuroendocrine system. They can arise in various organs, most commonly in the gastrointestinal tract, pancreas, and lungs. Based on differentiation and proliferation rate, NETs are classified into grades 1 to 3, with grade 3 tumours showing higher proliferative activity. Gastroenteropancreatic NETs (GEP-NETs) account for the majority of cases, while lung-NETs are the most frequent non-GEP-NETs. Treatment strategies vary depending on tumour location, grade, and other clinical factors, and include somatostatin analogues, targeted therapies, peptide receptor radionuclide therapy (PRRT), and chemotherapy. Cabozantinib is a multi-tyrosine kinase inhibitor targeting mesenchymal-epithelial transition							

factor (c-MET), vascular endothelial growth factor receptor kinases involved in tumour progression. It has been approved in the European Union (EU) for several indications, including renal cell carcinoma, hepatocellular carcinoma, and differentiated thyroid carcinoma. In 2025, cabozantinib received EU approval for the treatment of unresectable or metastatic, well differentiated pancreatic (pNET) and extra-pancreatic NET (epNET) who have progressed following at least one prior systemic therapy other than somatostatin analogues. In the phase III CABINET trial, cabozantinib significantly prolonged progression-free survival (PFS) compared to placebo in patients with advanced, well-differentiated pNET and epNET, with median PFS of 13.8 and 8.4 months, respectively. This non-interventional study aims to evaluate the real-world effectiveness and safety of cabozantinib in patients with NETs. It will also assess the impact of dose modifications on treatment duration, explore quality of life outcomes, and collect data on prior and subsequent therapies.

Study Timelines

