 QLQ-C30 global and subscale scores for each visit at which
 hrOoL was assessed.
- QLQ-GINET21 subscale scores for each visit at which hrQoL was assessed for GI-NET participants.
- Incidence of all AEs, all nonserious, drug-related AEs and all serious AEs, overall and by grade and causality.
- Frequency of dose interruptions, dose reductions and treatment discontinuations, specifically due to AEs.
- DoT: defined as the time from first dose until last dose of cabozantinib.
- Frequency overall and by type of therapy switch (defined as permanent discontinuation of cabozantinib treatment within the cabozantinib treatment phase and start of a next line of treatment (LoT) as well as nature of next LoT).
- DCR of next LoT: proportion of participants who achieve CR, PR or SD determined based on routine radiographic response assessments approx. 3 months after switch to next line of therapy after cabozantinib.
- Evolution of NET biomarkers such as Chromogranin A (CgA) and Neuron-Specific Enolase (NSE) during the treatment period.

PAGE 7/52

- TTNT, defined as time from first dose of cabozantinib until first dose of subsequent therapy.
- PFS during cabozantinib treatment phase, defined as time from first intake of cabozantinib until PD (as assessed by the investigator per radiological and/or clinical tumour assessment) or death from any cause, whichever occurs first.
- Rate of progression-free survival at 12 months and 18 months.

Exploratory endpoints

- Assessment of nature and proportion of participants receiving the different measures at each visit these measures were assessed..
- Assessment of a potential correlation between the investigated parameters, specifically:
 - Effectiveness outcomes and occurrence of AEs.
 - Effectiveness outcomes and dose reduction.
 - HrQoL and dose reduction.
 - HrQoL and supporting measures.
 - Supportive measures and DoT/treatment discontinuation due to AEs.
 - Dose reduction and DoT.
 - HrQoL and DoT.

Statistical Methods:

Based on the feasibility evaluation, it was estimated that 150 participants in approximately 50 sites could be enrolled in this study. No power calculations have been performed since this is a non-interventional study with a descriptive objective.

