Abbreviations: AE=Adverse Event; CR=Complete Response; DCR=Disease control rate; ECOG=Eastern Cooperative Oncology Group; eCRF=electronic Case Report Form; EORTC=European Organisation for Research and Treatment of Cancer; EoS=End of Study; FU=Follow-Up; HrQoL=Health-related Quality of Life; NETs=Neuroendocrine tumours; PD=Progressive Disease; PR=Partial Response; PSP=Patient Support Program; QLQ-C30=Core Quality of Life Questionnaire; QLQ-GINET21= Quality of Life Questionnaire module for GI-NET patients; SD=Stable Disease; TA=Tumour Assessment.

IPSEN GROUP CONFIDENTIAL CONFIDENTIAL

PROTOCOL FINAL V1.0: 30 JULY 2025 PAGE 22/52

All data will be recorded as applicable and available during standard of care routine: if a specific diagnostic procedure is done according to clinical routine the corresponding data should be recorded in the eCRF, otherwise the corresponding part of the eCRF will be marked as not done.

- ^a EoS visit for participants still on cabozantinib treatment after 18 months.
- ^b Combined FU/EoS visit for participants who discontinued cabozantinib early (up to 15 months after Visit 1) and subsequent therapy switch.
- ^c Enrolment in the study is possible if cabozantinib treatment started up to 4 weeks prior to enrolment. See Section 4.1.
- ^d Clinical and/or TA via imaging to determine SD, PR, CR and PD. The type of assessment must be recorded in the eCRF.
- ^e The baseline radiological tumour assessment should be the most recent TA prior to enrolment.
- ^f In case of PD and cabozantinib treatment discontinuation and subsequent therapy switch, only the FU visit must be performed 3 months after end of cabozantinib treatment. Of note, cabozantinib treatment beyond progress is possible; in this case the participant is not passed over to the FU period but remains in the 18-month observation period. In addition, also other reasons e.g. drug intolerability or adverse events might lead to cabozantinib treatment discontinuation and switch to subsequent treatment; in these cases, also only the FU visit must be performed 3 months after end of cabozantinib treatment.
- g Including recording of dose modifications, overdoses, treatment interruptions and permanent study discontinuations along with the reason for discontinuation.
- h Performed if participant was enrolled up to 4 weeks after first dose of cabozantinib and Visit 1 was captured retrospectively. HrQoL baseline will then be taken.

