4.6 Data Sources

Data for this study will be obtained via the following sources:

- Patient medical file: The investigator or authorised medical staff will record clinical and treatment data (if applicable) from patients' medical files into the eCRF at each collection time point, specified in Table 4-1.
- Tumour assessments: All tumour assessments are based on investigator's clinical and/or assessments by imaging. For radiological assessments tumour imaging data is provided by the radiologists. Data is recorded in the eCRF at each collection time point, specified in Table 4-1.

PAGE 27/52

- Quality of Life (QoL) questionnaire: EORTC QLQ-C30 (Version 3, German language) and QLQ-GINET21 (2006, German language) questionnaire data will be collected on paper-based questionnaires or electronic version if used per treatment routine in the site and completed by the participant at each collection time point. The investigator or authorised medical staff will record the data into the eCRF at each collection time point, specified in Table 4-1.
- NET Biomarkers: NET Biomarker data for CgA and NSE are provided by the centre's local laboratory and recorded in the eCRF at collection time points when available, specified in Table 4-1.

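### CgA and NSE are summarised only as raw levels at each visit, in a group that shrinks and changes, so the stated summary cannot isolate change within participants

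*Protocol*

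**What the plan says.** The objective is causal in tone: "To describe the potential impact of cabozantinib treatment on NET biomarkers". The Synopsis endpoint is longitudinal: "Evolution of NET biomarkers such as Chromogranin A (CgA) and Neuron-Specific Enolase (NSE) during the treatment period". Sections 3 and 6.1.2 word the endpoint more narrowly, as the level at each visit where the marker was assessed.

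The analysis in Section 8.4.3.2 follows the narrower wording. Levels of each marker "will be summarised for each visit by descriptive statistics providing n, mean, 95% CI of the mean", with StD, median, minimum and maximum. There is no change from baseline, ratio, paired comparison or scaling to a reference limit. Section 8.4.5, by contrast, specifies change from baseline for QLQ-C30 and QLQ-GINET21.

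On who is measured:
- Section 6.1.2 has "Determination of CgA and NSE levels by local labs as per local routine", so measurement depends on local habit.
- Table 4-1 marks the biochemical markers at Visits 1 to 9 and leaves the follow-up column empty.
- Footnote f to Table 4-1 leaves only the follow-up visit after progression with discontinuation and switch. For discontinuation and switch for other reasons it says "in these cases, also only the FU visit must be performed 3 months after end of cabozantinib treatment".
- Section 8.4 does not replace missing data.

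On the assays: "NET Biomarker data for CgA and NSE are provided by the centre's local laboratory" (Section 4.6), and "This study will be conducted in up to 50 centres in Austria and Germany" (Section 4.1).

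**The concern.** A row of visit means invites the reader to compare Month 6 or Month 12 with baseline. That comparison mixes two things: change within participants, and change in who is still being measured. The planned table cannot separate them. The median handles skew, but it is exposed to the same change of composition.

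The study has a single arm, so no comparator would reveal an artefact. A falling mean with a 95% CI beside it would readily be read as a drug effect on the markers, and this is the only biomarker analysis that the protocol names for that objective.

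A separate and smaller issue is that values from different local laboratories may not share an assay, unit or reference range. Pooling them on the raw scale then affects the levels and their spread.

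**Working it through.** The protocol states no expected value or precision for the biomarkers, so there is no figure of its own to reproduce here.

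**Step 1. How fast the group shrinks.** Section 2.3 cites median treatment durations of 8.3 months (pNET) and 5.5 months (epNET) from the phase III trial. Assume exponential stopping and the 7.3% pNET share in Section 8.5. The pooled median t solves 0.073 × 0.5^(t/8.3) + 0.927 × 0.5^(t/5.5) = 0.5, which gives t = 5.66 months. The proportion on treatment is then 0.5^(6/5.66) = 48% at Month 6 and 0.5^(12/5.66) = 23% at Month 12, or about 72 and 35 of 150. With the phase III mix of 64 pNET to 134 epNET (Section 8.3), about 77 and 40 remain.

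**Step 2. A small example (assumed marker values).** Take 75 participants constant at 100 with median duration 8.3 months, and 75 constant at 1000 with median duration 5.5 months.
- Baseline mean: (75 × 100 + 75 × 1000)/150 = 550.
- Month 6: 45.4 and 35.2 remain; mean (45.4 × 100 + 35.2 × 1000)/80.6 ≈ 493.
- Month 12: 27.5 and 16.5 remain; mean ≈ 438.

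The mean falls by 1 − 438/550 = 20% with no change in anyone.

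**Step 3. Range over the unknown link.** Assume marker = 100 × exp(sZ), constant over time, with Z standard normal, and a stopping hazard of λh^Z with λ = ln 2/5.66 = 0.1225 per month. Here h is the hazard ratio per SD of log marker. The visit mean relative to baseline is

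E[exp(sZ) × exp(−λt h^Z)] / {E[exp(−λt h^Z)] × exp(s²/2)}.

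With s = 1.5:

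| h per SD | Change in mean, Month 6 | Change in mean, Month 12 |
|---|---|---|
| 1/1.1 | +10% | +21% |
| 1.0 | 0% | 0% |
| 1.1 | −11% | −20% |
| 1.2 | −20% | −36% |
| 1.3 | −29% | −48% |

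At h = 1.3 the median falls by about 24% and 42%, so it offers no protection. Also at h = 1.3, varying s from 1.0 to 2.0 moves the Month 6 fall in the mean from 19% to 39%. Using the 64:134 mix instead gives 27% at Month 6 for s = 1.5.

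**Step 4. Cross-check in samples of 150.** With the 64:134 mix and s = 1.0, the simulated mean ratio to baseline at Months 6 and 12 is 0.85 and 0.73 at h = 1.25. At h = 1.0 it stays at 0.98 to 1.01 at every visit, with or without scale differences between laboratories (SD 0.5 on the log scale). Laboratory differences alone therefore produce no drift.

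**Step 5. The alternative.** In all these scenarios each participant's ratio to baseline is exactly 1.00 at every visit, whoever has left and whatever scale the laboratory uses, provided that participant stays with one laboratory.

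**Step 6. The interval.** For a log-normal marker and n = 72, simulated coverage of the nominal 95% CI of the raw mean is about 91%, 84% and 73% for s = 1.0, 1.5 and 2.0. This also rests on the assumed skew.

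**The case against.** The strongest reply is that the analysis matches the endpoint as Sections 3 and 6.1.2 define it, namely levels at each visit. Nothing is tested, n is shown at each visit so the shrinkage is visible, and Section 8 says that the SAP may change its content. Change-from-baseline tables and log transformation are often left to an SAP. This has weight, and it keeps the point modest. It does not remove it: the biomarker statistics are written out in full, the objective and the Synopsis endpoint are about impact and evolution, and the same section specifies change from baseline for quality of life.

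The model also removes everyone when the drug stops, whereas the footnotes to Table 4-1 move to follow-up those who discontinue and switch. Real attrition from the biomarker visits could therefore be slower than assumed.

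A reader might infer four stronger things that the protocol does not support:
- That participants with high markers do stop earlier. Nothing in the protocol links marker level to stopping; at a hazard ratio of 1.0 the effect is zero.
- That local laboratories cause the apparent fall. They make raw levels less comparable, but they shift the series only if the laboratory mix changes between visits.
- That the plan has no skew-robust summary. It lists the median, and the general rule in Section 8.4 adds the quartiles.
- That units and reference limits will not be captured. The eCRF is not shown, and Section 4.5 lists data categories, not fields.

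**Conclusion.** The point holds as a limit on what the stated summary can show: raw visit levels in a changing group cannot answer a question about impact or evolution. Confidence in that is high, because it follows from the protocol's own collection schedule and cited treatment durations.

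Confidence in the size is low. The marker's distribution, exponential attrition and the link between level and stopping are all assumptions. Within the range examined, the artefact runs from nothing to a fall in the mean of about half at Month 12, and its direction is not known in advance. The primary endpoint is unaffected. This is a cheap improvement to one descriptive secondary analysis and should be made.

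**What to change.** In Section 8.4.3.2:
- Add, as the main biomarker summary, the within-participant ratio to baseline on the log scale (geometric mean ratio with 95% CI) at each visit, among participants with a baseline and a visit value from the same laboratory.
- Show n at each visit, and the baseline levels of those still contributing.
- Keep the raw median and quartiles as supportive, and do not rely on the CI of the raw mean.

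Make sure that the unit and the local upper limit of normal are recorded with each value.

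The cost is a changed table and, if the eCRF lacks them, two fields per marker. No additional test is needed, so the non-interventional design is unaffected. Participants without a baseline value leave the ratio table. The ratio also still describes only those remaining on treatment: if participants whose marker rises stop sooner, the remaining pairs will look favourable. The report should say so.
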